The typical range from highest threshold luminance to absolute rod threshold covers about 5 logarithm units of luminance [16]. The first part of the curve is the photopic phase, which identifies the cone adaptation. The last part of the curve is the scotopic phase, which identifies the rod adaptation [11]. The interval between the two phases is commonly referred to as the rod-cone break. It can be seen in Figure 1 that, as the luminance is reduced, there is an increase in light sensitivity, which is initially very rapid before levelling off after 5 to 10 minutes at the final or absolute cone threshold [5]. At this point, the foveal cone cells are fully dark adapted (i.e., they have reached their maximum sensitivity [17]); in contrast, the rod cells are saturated and inactive [1]. With time (the luminance of the stimulus is reduced) a second slower fall in the threshold luminance is observed as the peripheral rod cells become activated (rhodopsin is regenerated). Rod adaptation is slower than the cone adaptation [18] because of the regeneration half-life of the visual pigments. However, unlike cone cells, light of very low intensity is capable of stimulating the rod cells, when given sufficient time to accumulate rhodopsin [2]. After approximately 30-40 minutes in total darkness, the final rod threshold is achieved. Dark adaptation is now complete and no further increase in sensitivity of the rods photoreceptors is possible.

The time required to reach maximum sensitivity is dependent on the amount of pigment bleached by the previous light exposure [19] and neural adaptation. The wavelength of the incident light has also a strong influence on the dark-adaptation curve, given that cone mediated vision is responsible for colour vision whereas rod vision is colourless.

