- II. Do the threshold measurements in the elderly compare with literature data adjusted to exclude aged crystalline lens and pupillary miosis contributions?
- III. Are test results from the novel light-emitting system repeatable?
- IV. If the results are not repeatable, can any assumption be made about reducing their variability through software and/or hardware optimisation of the novel light-emitting system?

V. Is the novel light-emitting system comfortable and easy to use by normal healthy adults despite age differences?

4. Method

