The Smith-Kettlewell Institute Low Luminance (SKILL) card will be used to measure spatial vision under conditions of reduced contrast and luminance. The SKILL card consists of two near acuity charts mounted back to back. One side of the card contains black letters on a dark grey background (designed to simulate reduced contrast and luminance conditions) whilst the other side has a high-contrast, black-on-white letter chart. Using the appropriate near correction each card will be successively presented at a distance of 40 cm. The SKILL score will be recorded as the difference in performance (number of letters) between the two cards.

Contrast sensitivity

Contrast sensitivity will be measured using a Near Pelli-Robson Contrast Sensitivity Card. The card uses the traditional optotypes found in the original Pelli-Robson chart (i.e., 6 letters per line arranged in groups of 3 with a decreasing contrast) but features an overall size of 22.86 x 29.53 cm. Using the appropriate near correction, subjects will read the letters from a distance of 40 cm, starting with the highest contrast, until they are unable to read two or three letters in a single group. A score is assigned based on the contrast of the last group in which two or three letters were correctly identified.

Pupillometry

Pupil size will be measured manually (with a ruler) in the same room where the visual assessment was performed, under a known level of illumination.

Confrontational visual fields

To examine the visual field of the right eye the examiner will ask the subject to cover their left eye using the palm of their hand and instruct them to look at a pen located in front of them (held by the examiner). The examiner will use a slowly wagging finger to check the extent of the subject's visual field superiorly, inferiorly, nasally, temporally and on the diagonals. The subject must indicate when the examiner's finger comes into view. The same procedure is used to test the visual field of the left eye, covering the right eye.

This test will only pick up large visual field defects.

Direct ophthalmoscopy

Direct ophthalmoscopy is a non-invasive technique used to examine the posterior pole of the eye (fundus). A beam of light is shone into the eye through the pupil using an instrument called ophthalmoscope (a device about the size of a flashlight). Using an ophthalmoscope the examiner can detect pathological changes in the retina such as abnormal blood vessels or haemorrhages.

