Dark-adaptometry testing will be carried out by using the novel investigational system described in Section 4.3. Wearable goggles and joystick are given to participants in their switched-on status and held by the subject under test respectively on the forehead, with an elastic strap, and on the dominant hand. For hygienic safety purposes, a non-allergenic disposable tissue will be placed on top of the inner gasket of the goggles that will be in contact with participants' face. Where a disposable tissue would not be available, the inner gasket of the goggles will be accurately cleaned with a sterile isopropanol solution. Participants will sit comfortably throughout the test and wear disposable earphones playing music to drown out external noise and any auditory signals from the embedded electronics when light stimuli are emitted. Testing is non-invasive and is semi-automatic in that the subject under test is required to collaborate actively during the procedure in order to start it and go through it. A responsible collaboration throughout the test will be repeatedly encouraged as testing results are strictly based on the subject's response. The examiner will start the test by triggering a white flash of light through a standard camera flash (e.g., Canon Speedlite 540EZ – Guide Number 54, 1.2 ms duration). The flash will be channelled to the study eye and aims to photo-bleach, hence reset the photoreceptors of the retina. Immediately after the onset of the photo-bleaching flash, the goggles are pulled down over the eyes by the user that will now be exposed to intermittent white light stimuli. Light stimuli are shone automatically inside the goggles after the photo-bleaching flash and until the end of the test. Dark-adaptometry testing will last for about 25-35

minutes and will involve one eye only. This will be randomly allocated by the examiner or will be the only eye meeting the inclusion criteria. As the brightness of the intermittent light stimuli changes throughout the test as well as the time at which they are presented, participants are asked to press either of the joystick's buttons to indicate when the light is visible. The intermittent light features an initial brightness of approximately 4.86 cd/m^2 and becomes dimmer and dimmer overall. The test lasts until participants will not be able to identify any new light stimuli.

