The absolute threshold will be the last measured threshold and recorded as the dimmest light that the subject can detect when the rod sensitivity of the study eye is maximum. In a healthy adult, the absolute threshold is typically equal to a logarithmic light intensity around 10^{-6} cd/m^2 at a time of around 30 minutes from the start of the test.

The examiner will monitor in real-time the testing results on a laptop, which is USB-connected to the frame of the goggles from the same side of the study eye. A best fit of collected threshold measurements will be calculated; from this fit, a biphasic curve is expected to be observed.

The rod-cone break will be identified as the point of phase-change in the calculated curve, which coincides with the point when rods become more sensitive than cones. In a healthy adult, the rod-cone break is typically equal to a logarithmic light intensity around 10^{-3} cd/m^2 at a time of around 7 minutes from the start of the test.

The slope of the rod-mediated response will be also calculated from the best fit of the collected threshold measurements. Particularly, the slope of the (second) S2 and (third) S3 rod-mediated component of recovery will be identified: these coincide with a long section of near linear slope following the initial rapid nonlinear increase in rod sensitivity.

An ad hoc pen-and-paper system usability questionnaire will be presented to participants twice upon completion of the first and the last dark-adaptometry testing visit. Participants will rate comfort and ease of use of the system on a scale of 1-10 through questions targeting hardware and software implementation as well as testing duration and expectations.

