Statistical Analysis Plan cover sheet

Wearable Dark-adaptometer in Normal Adult Healthy Volunteers

NCT number NCT02674425

Version 2.0 27/01/2017

WONDER STUDY
Evaluation of a novel wearable light-emitting system for measuring dark-adaptation thresholds in normal adult healthy volunteers

Statistical Analysis Plan

Chief Investigator: [name]
Principal Investigator: [name]
Co-Investigator: [name]
Collaborator: [name]

Clinical Eye Research Centre, St Paul's Eye Unit, Royal Liverpool University Hospital, [name]
University of Liverpool, Department of Eye and Vision Science, Institute of Ageing and Chronic Disease, [name]

Statistical Analysis Plan

Cone- and rod-mediated dark adaptation functions were expressed as log threshold luminance vs. time (minutes). The dynamics of participants' visual recovery after the bleach offset were determined by fitting established models of human dark adaptation to collected threshold data. Two models were used: 1) a bi-exponential model, fitting a single exponential function separately to the cone-mediated phase and the rod-mediated phase of dark adaptation; and 2) an exponential bi-linear model, fitting a single exponential to the cone threshold recovery data and 2 linear components (i.e., S2 and S3) to any rod threshold recovery data.

$$\begin{aligned}
 1) \quad D &= \underbrace{\theta_1 + \theta_2 \cdot \exp\left(\frac{-t}{\theta_3}\right)}_{\text{Cone}} + \underbrace{\eta_4 \cdot \exp\left(\frac{-(t - \theta_5) \cdot h(t, \theta_5)}{\eta_6}\right)}_{\text{Rod}} \\
 2) \quad D &= \underbrace{\theta_1 + \theta_2 \cdot \exp\left(\frac{-t}{\theta_3}\right)}_{\text{Cone}} + \underbrace{\theta_4 \cdot (t - \theta_5) \cdot h(t, \theta_5)}_{\text{S2}} + \underbrace{\theta_6 \cdot (t - \theta_7) \cdot h(t, \theta_7)}_{\text{S3}}
 \end{aligned}$$

$$h(t, \pi) = \begin{cases} 0 & \text{if } t - \pi \leq 0, \\ 1 & \text{if } t - \pi > 0. \end{cases} \quad h(t, \pi) = \frac{1}{(1 + e^{-k(t-\pi)})}$$

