Cone- and rod-mediated parameters were compared to previous literature on human dark adaptation to evaluate the performance of the developed dark adaptometer. Clinical data reported in [6] were particularly taken into consideration since a similar DA protocol was used by Jackson et al. to assess dark adaptation changes with age and as a function of decade. In addition, trial outcomes of interest were the test-retest and usability score results and variability obtained from participants after one or multiple DA visits.

Repeatability coefficient (RC) and within-case coefficient of variance (wCV) were calculated starting from the within-subject variance for each trial participant who completed at least 2 DA visits in order to assess variation in repeat measurements on the same patient. Intra-class correlation coefficient (ICC) – 2-way mixed-effects, absolute agreement, average measurement – was calculated for both

Group 1 and Group 2 through SPSS® Statistics V22.0 (IBM, Armonk, USA) to obtain the proportion of total variation in measurements by between-patient differences.

A pen-and-paper questionnaire as in Appendix 1-a was presented to participants twice on completion of the first and the third DA appointment. Seventeen questions targeting hardware and software implementation as well as personal feedback on the duration of the DA test were asked to rate comfort and ease of use of the developed system.

- [1] Alpern M. et al. Rhodopsin kinetics in the human eye. *Journal of Physiology*, 217 (1971), pp. 447-471.
- [2] W.A.H. Rushton, D.S. Powell. The rhodopsin content and the visual threshold of human rods. *Vision Research*, 12 (1972), pp. 1073–1081.
- [4] T.D. Lamb. Spontaneous quantal events induced in toad rods by pigment bleaching. *Nature*, 287 (5780) (1980), pp. 349-351.
- [5] T.D. Lamb. The involvement of rod photoreceptors in dark adaptation. *Vision Research*, 21 (12) (1981), pp. 1773-1782.

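### Question II sets uncorrected Group 2 thresholds against literature adjusted for lens and pupil, and the SAP does not say which literature values are used

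*Protocol*

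**What the plan says.** Question II appears in Protocol sections 1 and 3: "Do the threshold measurements in the elderly compare with literature data adjusted to exclude aged crystalline lens and pupillary miosis contributions".

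The SAP's comparison paragraph states: "Cone- and rod-mediated parameters were compared to previous literature on human dark adaptation to evaluate the performance of the developed dark adaptometer". Its main comparator is an ageing study: "Clinical data reported in [6] were particularly taken into consideration since a similar DA protocol was used". The paragraph does not say whether that study's adjusted or unadjusted values are meant, and it does not refer to question II.

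On the trial side:

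- Protocol 4.8 defines the level outcome directly from what the participant sees: "The absolute threshold will be the last measured threshold and recorded as the dimmest light that the subject can detect".
- The SAP's recovery parameters are "determined by fitting established models of human dark adaptation to collected threshold data". Neither model equation has an optical term.
- The one pupil measurement is described in Protocol 4.8: "Pupil size will be measured manually (with a ruler) in the same room where the visual assessment was performed, under a known level of illumination". Section 4.9 schedules it once, at baseline, and section 4.13 lists it as a variable in mm. No stated analysis uses it.
- Protocol sections 4.3 and 4.7 to 4.9 list no dilation, artificial pupil or lens measurement. Section 4.14 gives no analysis method.

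**The concern.** A comparison with literature separates device error from other causes only if both sides are on the same optical footing. Question II itself treats the aged lens and the small pupil as contributions to be removed, and section 2 of the Protocol names pupil size among the determinants of dark adaptation. Removing these contributions from one side only leaves a systematic difference that more participants would not reduce.

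Absolute threshold is one of two primary outcomes (Protocol 4.11), and the SAP gives evaluation of the device as the purpose of the literature comparison. Two wrong readings are possible: an accurate device could appear to read high in Group 2, or a device that reads too low could appear to agree. Repeatability and usability results are not touched.

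**Working it through.** The documents give no SD, agreement limit, pupil diameter or lens density, so there is no planned figure to reproduce. The check has two parts.

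**1. Basis on each side**

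| | Literature side | Trial side (Group 2) |
|---|---|---|
| Question II | adjusted for lens and miosis | no adjustment mentioned |
| SAP comparison paragraph | not stated | not stated |
| Procedures (Protocol 4.3, 4.7 to 4.9) | – | no dilation, artificial pupil or lens measure; ruler pupil in a lit room |
| SAP models | – | fitted to thresholds as collected |

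The ruler reading could not supply a correction later. It is taken under room illumination, and the thresholds are measured inside blacked-out goggles.

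**2. Scale, on assumed inputs**

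On the log scale, observed threshold = retinal threshold + optical loss + device error. Against adjusted literature, the expected Group 2 difference is therefore optical loss + device error. With zero device error it equals the optical loss. If the device reads low by the same amount as the loss, the difference is zero. A constant loss moves the absolute threshold and the cone plateau by the same amount and leaves the slopes of the fitted curve unchanged.

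Pupil term: retinal illuminance is proportional to pupil area, so loss = 2·log10(d_reference / d_older).

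| Assumed diameters, mm (reference v older) | Loss, log units |
|---|---|
| 6 v 5.5 | 0.076 |
| 6.5 v 5.5 | 0.145 |
| 7 v 5 | 0.292 |
| 6 v 4 | 0.352 |

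Lens loss would add to these. The documents give no figure for it and none is added here.

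Yardstick: Group 2 has n = 10 (Protocol 4.4). The 95% half-width of its mean is t(0.975, 9)·SD/√10 = 2.262·SD/3.162 = 0.715·SD.

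| Assumed SD, log units | Half-width, log units |
|---|---|
| 0.2 | 0.143 |
| 0.3 | 0.215 |
| 0.4 | 0.286 |

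At SD 0.2, a loss of 0.076 lies inside the half-width, 0.145 about equals it, and 0.292 and 0.352 exceed it. At SD 0.4, 0.076 and 0.145 lie inside, 0.292 about equals it, and 0.352 exceeds it. These half-widths treat the literature mean as fixed. Sampling error in the literature mean would widen them.

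**The case against.** **The mismatch is conditional.** The operative text is the SAP paragraph, which plans no adjusted comparison. It describes its main comparator as a study of change with age, by decade. If unadjusted values for the same ages are used, similar optics sit on both sides and the mismatch goes away. This stands. A reader might infer that the trial's comparison is biased as planned. The documents do not support that, because they do not show which values are used or whether the comparator reports adjusted ones. Question II as worded would then go unanswered, so the basis still has to be stated.

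**Question II may have meant adjustment on both sides, or may not concern the device.** The first reading is possible, but no text plans such a step. On the second, question I is the direct device question. However, the SAP applies device evaluation to its literature comparison in general and makes no exception for Group 2.

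**Group 1 gives a check.** Ten people aged 18 to 40 use the same device. A uniform device error would appear in both groups, whereas age-related optical loss would appear mainly in Group 2. This stands in part. It weakens any claim that optical loss must be taken for device error, but the contrast is informal, rests on 10 people per group, and is not written into the plan.

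**Timing.** A reader might also infer that less light reaches an older retina at the bleaching flash, so that the time of the rod-cone break is biased too. The documents do not support adding this. The flash is given before the goggles come down, so losses in the dark do not carry over. The bleach received by the comparator's participants is not described, and the direction of any shift is undetermined. It is a separate matter from the adjustment of literature thresholds.

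**Conclusion.** The point holds in conditional form. Question II names a one-sided comparison, nothing in either document corrects the trial thresholds, and the SAP leaves the basis of the literature values open. If adjusted values are used, Group 2 levels are expected to sit above the comparator by the optical loss even with an accurate device, and a device reading low could be masked.

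On assumed diameters the pupil part is about 0.08 to 0.35 log units, against a half-width of 0.14 to 0.29 log units at assumed SDs of 0.2 to 0.4. The offset may therefore be hidden by sampling error or exceed it. All these inputs are assumptions, so the figures give scale only. This should be corrected because it bears on a primary outcome and a stated research question. It does not invalidate the study.

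**What to change.** Reword question II and the SAP comparison so that both sides share one stated basis, and name the literature values used.

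1. Compare uncorrected Group 2 levels with unadjusted, age-matched literature values where these are published.
2. Otherwise, apply to the trial thresholds the same stated age-based lens and pupil correction that was used for the literature values, and report corrected and raw results side by side. Do not use the lit-room ruler reading as the dark-adapted pupil.
3. If neither is possible, state that a Group 2 level difference from adjusted data will not be attributed to the device, and report the Group 1 comparison beside it as a check on uniform device error.

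Cost: options 1 and 3 need wording only. Option 2 is a small reanalysis of the thresholds already stored as data points (Protocol 4.3 and 4.13). No option needs new participants, visits or measurements. The downsides are that unadjusted values may not be published, that a published correction carries its own error, and that option 1 replaces question II instead of answering it as now worded.

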4.1. Study design

Single-centre, observational healthy case-only study.

4.2. Setting

The research will take place at the Clinical Eye Research Centre (CERC) of St. Paul's Eye Unit at the Royal Liverpool University Hospital, Liverpool (UK).

4.3. Investigational system

[figure not shown]

Figure 3. 3-D model of the head-mounted goggles with parts

The novel dark-adaptometer is designed as a wearable and semi-automated system consisting of a pair of head-mounted goggles (Figure 3) and a handheld joystick. Within each side of the goggles are included: an organic light emitting diode (OLED) display, which delivers the light stimuli; and a LCD filter sitting in front of the display to precisely tune the light stimuli within a range between 10^{-6} to 10 cd/m^2 . A handheld joystick completes the system allowing the subject under test to wireless transmit its response to the visible light stimuli through the press of a button. The response is cached and interpreted by the computing unit inside the goggles, which automatically set light intensity and time interval of the successive stimuli based on a modified 3-down-1-up staircase procedure described as in [43] and schematically depicted in Figure 4.

[figure not shown]

Figure 4. Flow-chart of the implemented dark-adaptometry testing procedure

Wearable goggles and joystick are given to participants in their switched-on status and held by the subject under test respectively on the forehead, with an elastic strap, and on the dominant hand. In order to reset the photoreceptors of the retina, thus guarantee a similar non-dark-adapted background common to all participants, a photo-bleaching flash is presented through an external camera and channelled to the study eye at the start of the test. Immediately after the onset of the photo-bleaching flash, the goggles are pulled down over the eyes by the user that will now be exposed to white light stimuli of 200 milliseconds duration. Light stimuli are automatically emitted for the threshold measurements and will stop when the absolute threshold is measured, which in normal healthy adults typically occurs after 25-35 minutes from start.

Such a system implementation aims to be easy to use and operate avoiding the use of any skilled operator. In addition, the system requires minimal user training. Data are digitally stored

as a .csv file into a preselected memory location of a USB-connected PC and real-time plotted through an ad hoc graphical user interface. The novel light-emitting system is very versatile and uses low-power and low-cost solid-state electronics. Power is independently supplied via USB to each side of the goggles, thus enabling dark-adaptometry testing independently on each eye, and by mean of a single AAA rechargeable battery to the handheld joystick.

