However, there are significant disadvantages and limitations inherent in currently used dark adaptometers including:

- 1) the use of old and out dated technology;
- 2) most adaptometers are elaborate, large, heavy, non-portable and expensive;
- 3) test procedures require full attention of highly trained operators in a clinical environment;
- 4) electrical supply is provided by mains, thus making them immobile and unsuitable for field investigations;
- 5) the operator must carry out the test in total darkness with the subject under test;
- 6) test data acquisition is manually obtained by the operator;
- 7) data analysis is complex requiring additional operator time after the test has terminated;
- 8) frequently, only one area of the retina may be tested at any one time;
- 9) there is a test learning curve leading to the possibility of biased results.

The need for an entirely dark room is also a physical limitation and an economic burden for the use of most of the modern portable-adaptometer instruments such as the scotopic sensitivity tester-1 (SST-1) (LKC Technologies) and the AdaptDx (MacuLogix). The SST-1 instrument entered the market as an efficient device for quickly identifying night-blindness in patients with retinal degeneration. However, several drawbacks have been identified when testing with the SST-1 including: the narrow range of measurable intensities (3.0 logarithmic units); the too dim luminance at its maximum intensity in order to evaluate subjects who had severe scotopic

sensitivity losses (floor effect); the too bright luminance at its minimum intensity in order to evaluate thresholds in subjects with good scotopic sensitivity (ceiling effect); the non-adequate initial adapting light for photopigment bleaching. In addition to standard dark-adaptometry testing, the AdaptDx is claimed to allow for early AMD diagnosis but this use is to date restricted to research purposes only.

For the reason listed above, conventional dark-adaptometers are unsuitable as a mass screening tool; consequently, dark adaptation is not routinely used as a clinical technique because of the practical problems it presents [33, 39-42].

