where θ_1 is the absolute cone threshold at time t after cessation of the bleach; θ_2 is the cone coefficient; θ_3 is the time constant of cone recovery referred to as cone τ ; η_4 is the final rod threshold or rod absolute sensitivity; θ_4 is the slope of the second rod phase (S2), which represents the rate limited restoration of photopigment; θ_5 is the rod-cone transition time from bleach offset or α point; η_6 is the time constant of rod recovery; θ_6 is the slope of the final component (S3) of rod recovery; θ_7 denotes the time from bleach offset to the transition between the second and final components of rod recovery, referred to as β point; and h is a switch function as described.

Both models, respectively as in Eq. 1 and Eq. 2, have previously been shown to provide a suitable approximation of cone and rod photopigment regenerations after near total photopigment bleaches [1–3]. Matlab (The MathWorks, Natick, USA) was used to fit the dark adaptation models to collected data.

For the cone-mediated dark adaptation function, a single exponential fit was used to estimate the cone time constant (τ) and cone sensitivity parameters. The cone τ is the time constant of the exponential model and is an estimate of cone sensitivity recovery speed. The cone sensitivity is the plateau of the exponential function and is an estimate of the absolute threshold of cone photoreceptors.

For the rod-mediated dark adaptation function, the parameters of interest were the rod-cone break (RCB), rod slope, and rod sensitivity. The RCB is the time in minutes after bleach offset at which the rods are more sensitive to the test target than the cones. The rod slope is the slope of the sensitivity recovery during the second (S2) and third (S3) components of rod-mediated dark adaptation described by Lamb et al. [4,5]. The rod sensitivity parameter was measured as the minimum sensitivity value of the rod-mediated dark adaptation function around the 40 minutes end of the test.

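### The dimmest stimulus equals the protocol's typical healthy absolute threshold, and the SAP makes no allowance for values known only to be at or below that limit

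*Protocol*

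**What the plan says.** Protocol 4.3 describes the display as having "a LCD filter sitting in front of the display to precisely tune the light stimuli within a range between 10^{-6} to 10 cd/m^2". Protocol 4.8 (Dark-adaptometry testing) states: "In a healthy adult, the absolute threshold is typically equal to a logarithmic light intensity around 10^{-6} cd/m^2". It defines the absolute threshold as the last threshold measured in the test. Protocol 4.11 lists absolute threshold as one of two primary outcomes, and 4.4 recruits only healthy volunteers, 10 in each of two age groups, each tested three times.

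A Background figure points in a different direction: "The typical range from highest threshold luminance to absolute rod threshold covers about 5 logarithm units of luminance". The starting level is in 4.8: "The intermittent light features an initial brightness of approximately 4.86" cd/m². The stepping procedure is "based on a modified 3-down-1-up staircase procedure described as in [43] and schematically depicted in Figure 4"; that figure is not shown in the text available to us.

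The SAP says rod sensitivity was "measured as the minimum sensitivity value of the rod-mediated dark adaptation function around the 40 minutes end of the test". On repeatability: "Repeatability coefficient (RC) and within-case coefficient of variance (wCV) were calculated starting from the within-subject variance for each trial participant" with at least two visits, plus an ICC for each group. It does not name the variables to which these measures apply. Nothing in the SAP text says how to analyse a test that ends with the dimmest stimulus still seen.

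**The concern.** A threshold cannot be measured below the dimmest light the device can show. A participant who still sees that light has a threshold known only to be at or below the limit, which makes it a left-censored value. If it is analysed as an ordinary measurement, two things follow. The mean moves towards poorer sensitivity, which affects the comparison with literature (research question I). Repeat visits by a sensitive participant also bunch at one value, so within-subject variance and RC shrink and the device appears more repeatable (question III). The second error favours the device under evaluation.

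The protocol recognises this kind of limit in its Background, where it faults a commercial adaptometer for "the too bright luminance at its minimum intensity in order to evaluate thresholds in subjects with good scotopic sensitivity (ceiling effect". The other primary outcome, the rod-cone break, is put near 10^-3 cd/m², three log units above the limit, and is not in question.

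**Working it through.** There is no figure of the plan's own to reproduce: neither document gives an SD, or a rate of tests at the limit.

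**Margin on the log10 scale.**
- Protocol 4.8 reading: typical threshold −6, display limit −6, margin −6 − (−6) = 0.
- Background reading: if the five log units are counted down from the 4.86 cd/m² start (an assumption, since the protocol does not say where counting begins), log10(4.86) − 5 = 0.69 − 5 = −4.31. The margin is −4.31 + 6 = 1.69 log.

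**Model (assumed).** Log threshold = mean + subject effect + visit effect, both normal, three visits. Values below −6 are recorded as −6. With between-subject SD b and within-subject SD w, the total SD is s = √(b² + w²).
- Share of tests at the limit = Φ((−6 − mean)/s).
- RC = 2.77 × within-subject SD.

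**Share at the limit and bias.** At a true mean of −6.0 the share is Φ(0) = 50%, or 30 of 20 × 3 = 60 tests if both groups share that mean. The bias is 0.399 × s: 0.399 × √(0.04 + 0.01) = +0.09 log at the smallest s and 0.399 × √(0.09 + 0.09) = +0.17 log at the largest. At −5.7 the share runs from Φ(−0.3/0.224) = 9% to Φ(−0.3/0.424) = 24%. At −5.5 it is 1–12%, and at −5.0 under 1%.

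**RC recorded as a fraction of true RC** (simulation, within-subject variances pooled over subjects):

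| b / w | −6.0 | −5.7 | −5.5 | −5.0 |
|---|---|---|---|---|
| 0.2 / 0.1 | 0.657 | 0.940 | 0.991 | 1.000 |
| 0.2 / 0.2 | 0.625 | 0.892 | 0.970 | 1.000 |
| 0.2 / 0.3 | 0.608 | 0.842 | 0.933 | 0.998 |
| 0.3 / 0.2 | 0.644 | 0.859 | 0.942 | 0.998 |
| 0.3 / 0.3 | 0.625 | 0.822 | 0.910 | 0.992 |

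For example, with w = 0.2 and b = 0.2 the true RC is 2.77 × 0.2 = 0.554; at −6.0 it is recorded as 0.346, and 0.346/0.554 = 0.625. RC is therefore 34–39% too small at −6.0, 6–18% at −5.7, 1–9% at −5.5 and under 1% at −5.0. The remaining combination, 0.3/0.1, gives 33%, 11% and 4% at the first three means. At −4.31 there is no effect.

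**Other choices.** With SDs of 0.2/0.2, 0.3/0.2 and 0.3/0.3 and a mean of −6.0:
- Dropping the limit tests leaves RC 22–29% too small with bias +0.22 to +0.33.
- Recording them 0.1 or 0.3 log above the limit makes RC 40–49% too small with bias +0.16 to +0.32.
- Replacing the last threshold by the minimum of a fitted rod curve, as the SAP does, leaves RC 30–39% too small at −6.0 and 2–10% at −5.5, under assumed curve shapes and noise.

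So the direction of error in the mean does not depend on which of these recording rules applies, and the direction of error in RC does not depend on any of the three choices.

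**The case against.** The strongest case against the point is that its size is unknown.
- The 10^-6 in Protocol 4.8 is qualified as approximate, and material distortion needs a true mean within roughly 0.3 log of the limit. The Background range would put the threshold well clear of it. This stands, and it is why the point is conditional.
- The SDs, the value recorded at the limit, and the application of RC, wCV and ICC to absolute threshold are all assumptions. This also stands.
- Figure 4 or the cited ageing study may say what the staircase does at its lowest step, so a reader who infers that the protocol has no such rule goes beyond the documents. A rule for running the test would still not say how the resulting value is analysed, and the point concerns only the analysis.
- The comparison with the commercial adaptometer should not be pressed. That device is also criticised for a range of 3.0 log units, whereas this one spans 7 (from −6 to 1). But a wide span does not show that the lower end is low enough.
- The steering committee reviews first-visit plots (Protocol 4.13) and could notice a plateau at the limit. No analysis step follows from that review.

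**Conclusion.** The point holds as a conditional gap in the SAP. On the protocol's own figures there is no stated margin between the typical value of a primary outcome and the dimmest stimulus, and the planned summaries treat every value as fully measured. If limit values are recorded as −6, the assumed SDs make RC about a third or more too small at a true mean of −6.0 and leave it essentially unaffected at −5.0 or above.

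A reader might infer that about half the tests will end at the limit, or that the absolute threshold cannot be measured with this device. The documents do not support either. The 50% share follows only if the true mean is exactly −6.0, and the Background figure is compatible with no tests at the limit at all. The change is worth making because the error would favour the device and the check is cheap, not because harm has been shown. Confidence is medium.

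**What to change.** In the SAP:
1. From the stored .csv files, flag each test whose final (last measured) threshold, as defined in Protocol 4.8, equals the dimmest available level. Report the count by group and visit. Do not flag on an isolated detection of the dimmest stimulus earlier in the test. In a check at a true mean of −5.7, that rule flagged 26–48% of tests when 14–21% were truly below the limit, against 13–22% for a flag on the final threshold. Censoring the extra tests would inflate RC.
2. If no test is flagged, the planned analysis stands.
3. If any is flagged, report the planned mean, RC, wCV and ICC for absolute threshold with a caveat that the display limit affects them. Add a sensitivity analysis of the final threshold that treats only the flagged values as left-censored at the limit, for example a random-intercept Tobit model with a group term.
4. Reconcile the end-of-test descriptions with the display limit. Protocol 4.3 ends the test when the absolute threshold is measured, 4.8 when no new stimulus can be identified (which needs a stimulus that is not seen), and the SAP refers to about 40 minutes.

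The cost is one flag per test from data already stored and, only if flags occur, one extra model. That model relies on normality and is imprecise with 20 people: at a true mean of −6.0 and a true RC of 0.55, its RC ran from 0.41 to 0.69 (10th to 90th percentiles), against a median of 0.35–0.36 with limit values set to −6. The SAP should state this imprecision and keep the model as a sensitivity analysis.
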